15.2.1. Summary of study data

All continuous variables will be summarised using the following descriptive statistics: n (non-missing sample size), mean, standard deviation, median, 25 percentile, 75 percentile, maximum and minimum. The frequency and percentages (based on the non-missing sample size) of observed levels will be reported for all categorical measures. For variables marked “binary” exact (Clopper-Pearson) 95% confidence intervals will be calculated where appropriate. For categorical variables with more than 2 categories 95% confidence intervals will be calculated using Goodman’s method [33].

In general, all data will be listed, sorted by site and patient, and when appropriate by visit number within patient. All summary tables will be structured with a column for each treatment pattern in the pre-defined order and will be annotated with the total population size relevant to that table/treatment pattern, including any missing observations.”

Patient Disposition

Data regarding how many patients reached the various stages of the study, how many dropped out, discontinued the treatment and for what reasons (death, ADRs, treatment failure, withdrew consent, lost to follow-up) will be presented for each subgroup and for study in bulk. Standard CONSORT diagram describing study patient flow will be provided.

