15.2.4. Potential study biases

The study limitations are those inherent to uncontrolled observational studies. Taking into account observational and uncontrolled nature of the study, fully evaluating of non-biological /biological treatment effectiveness will not be available. However, data regarding in real-life practice will be gathered and analyzed. The inclusion criteria are those that used when administering non-biological /biological treatment in practice and therefore, the same criteria as those that would have been used if we had performed a similar prospective study. This type of experimental design should prevent selection bias that could occur when patient enrollment is related to the development of the outcome. In prospective observational study like this attrition bias is possible, however, in case of early leaving study last data will be gathered and effectiveness will be estimated, these cases will not be excluded from effectiveness analysis.

Details of the statistical analyses will be presented in the Statistical Analysis Plan.

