**Table 1 Tabulated overview of visits and procedures**

The documentation of study data will be reported by investigators via electronic case report form (eCRF).

Assessment / Procedure	Retrospective data collection*	Baseline visit (V1, Day 1)	Observational visit (V2, Month 6)	Final visit (V3, Month12)
Informed consent		X		
Patients' eligibility assessment: Inclusion/exclusion criteria		X		
Date of visit		X	X	X
Demographics data		X		
Disability		X		
Physical examination		X	X	X
Medical history / Concurrent medical conditions	X	X		
History of IBD	X	X		
IBD family history		X		
IBD assessment	X	X	X	X
Disease activity data		X	X	X
IBD status		X	X	X
Laboratory and instrumental evaluation of IBD **	X	X	X	X
IBD treatment	X	X	X	X
Healthcare resources utilization	X	X	X	X
Concomitant treatment		X	X	X
Physician Survey		X		X
Adverse events			X	X

\* Retrospective data within two years before of patient enrolment in the study will be collected at Visit 1 after the signing of the informed consent form

\*\*All examinations (laboratory tests and instrumental exams) are done in accordance with clinical routine practice and physician's decision. All examinations results should be registered in electronic CRF only if they are done in routine practice.

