### 5.3.2 Data collected at the Observational visit (V2) and Final Visit (V3)

Data to be collected directly on Observational visit (V2) and Final visit (V3):

- Date of visit (day, month, year);
- Type of visit: visit to physician office or distant contact;
- Physical examination: weight (kg), body mass index calculation;
- IBD assessment at the time of the visit:
  - Disease extent according to the following Montreal Classification categories;
- Disease activity data at the visit will consist of specified signs and symptoms depending on the disease type:
  - CD: abdominal pain severity, number of liquid stools per day, presence of an abdominal mass, endoscopic findings (if done), documented presence of CD complications, and Harvey Bradshaw Index or other documented disease activity scales (if applicable);
  - UC: frequency of stools/day, rectal bleeding, endoscopic findings (if done), physician global assessment of disease severity, and Mayo scores or other documented disease activity scales (if applicable).
- IBD status (with current/last available data by the date of the visit):
  - IBD status as judged by investigator (remission, incomplete remission, flare, others), nature of remission at the time of examination;
  - IBD flare(s);
  - Systemic (extra intestinal) IBD manifestations;
  - IBD complications;
  - Vaccination in accordance with IBD treatment guidelines.
- Laboratory and instrumental evaluation of IBD (if done within routine practice);
- IBD treatment;
- IBD surgical treatment;
- Healthcare resources utilization;
- Concomitant treatment;
- Adverse events and adverse drug reactions (seriousness, severity, causality, start and stop dates, action, frequency, outcomes):
  - adverse drug reactions on IBD treatments;
  - adverse events on Entivyo® (Vedolizumab) treatment;
  - serious adverse events on IBD treatments (including Entivyo® (Vedolizumab) treatment).

All adverse events and adverse drug reactions must be documented on the Adverse Report Form which is appended to the Case Report Form.

Protocol ID	MACS-2017-102279	STATISTICAL ANALYSIS PLAN	Page 13 of 41	
IP	N/A		Date	30.12.2021
ID	MACS-2017-102279_SAP		Version	v1.2 final

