#### Secondary endpoints (outcomes):

- Distribution of socio-demographic variables in patients with moderate to severe UC/CD treated with biologics or/and non-biological treatment;
- Distribution of clinical variables in patients with moderate to severe UC/CD treated with biologics or/and non-biological treatment. Clinical characteristics include family history of IBD, smoking habits (no smoker, ex-smoker and current smoker), medical history comorbidities, disease characteristics (age of disease onset, location of disease, clinical course, disease severity, intestinal and systemic (extraintestinal) manifestations, complications in history and during the study observational period, etc.);
- Description of methods used for documentation of disease activity in routine practice (incl. clinical, endoscopic, lab, histological), and frequency of objective CD/UC disease activity assessment using different methods;
- Percentage of moderate to severe IBD patients achieved clinical and combined clinical and endoscopic remission (based on T2T definitions);
- Percentage of patients with moderate to severe IBD with at least one episode of failure of biological therapy or/and non-biological therapy (e.g., dose escalation of biologics, switching to another therapy, IBD-related surgery, medication augmentation);
- Patterns of treatment decisions\actions made after making the clinical assessment of IBD activity (incl. therapeutic de-escalation, escalation, without changes) depending on scenario of achievement /non-achievement of T2T treatment goals;
- Challenges of implementing a T2T strategy in UC and CD in real clinical practice (incl. clinicians related factors, patient related factors, disease related factors);
- Healthcare resources utilization for patients with moderate to severe UC/CD: hospitalizations due to complications, IBD related surgeries, disability determination

Protocol ID	MACS-2017-102279	STATISTICAL ANALYSIS PLAN	Page 16 of 41	
IP	N/A		Date	30.12.2021
ID	MACS-2017-102279_SAP		Version	v1.2 final

(frequency, percentage of UC and CD patients, who used these healthcare resources) within 2 years before enrolment and during 12-months observational period;

- Percentage of UC and CD patients with surgical treatment in 2 years history and during 12-months observational period in frames of this study: indications, types of surgeries, complications.

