## 8 STATISTICAL DATA PROCESSING

### 8.1 Statistical methods

#### 8.1.1 General information

Statistical analysis will be conducted using the software package Microsoft R Open version 4.0.2 from Microsoft R Application Network (MRAN) (<https://mran.microsoft.com>). Exact version of the software will be determined at the time of first interim analysis and will remain unchanged throughout the study. Version control for the software and related R packages used for statistical data processing will be performed using the CRAN Time Machine from Microsoft (or the purpose of reproducibility, MRAN hosts daily snapshots of the CRAN R packages and R releases as far back as Sept. 17, 2014). Statistical analysis will take data type and scale for each parameter when describing and analyzing the data.

Quantitative data (both continuous and discrete, if applicable) will be presented using the following parameters:

- Number of non-missing observations (n);
- Arithmetic mean (M);
- Standard deviation (SD);
- 95% confidence interval for the mean (95% CI);
- Median (Me);
- 25th percentile;
- 75th percentile;
- Minimal value (min);
- Maximal value (max);

Qualitative data including binary and categorical variables will be presented as number of cases per category, frequency for the category (relative to the non-missing number of observations), as well as 95% exact binary confidence interval calculated using Clopper-Pearson method (binary data) or Goodman method (categorical data).

Time-to-event data will be presented as median, 25th and 75th percentiles as well as graphically as Kaplan-Meyer survival curves with log-log 95% confidence intervals.

No statistical tests are planned for the primary endpoint of this study as all outputs will be purely descriptive. However, 95% significance level will be applied for all confidence intervals calculated, and exploratory statistical analysis will be conducted to identify statistically significant associations between treatment patterns and outcomes.

Medical history, concomitant conditions and adverse events will be coded using the MedDRA dictionary. As version of MedDRA is updated every six months, the first interim analysis will be conducted using the most current MedDRA version, and all subsequent analyses, including the

Protocol ID	MACS-2017-102279	STATISTICAL ANALYSIS PLAN	Page 23 of 41	
IP	N/A		Date	30.12.2021
ID	MACS-2017-102279_SAP		Version	v1.2 final

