#### 8.1.3 Assessment of secondary and exploratory endpoints

**Each original treatment combination** (defined as the treatment combination that was used by the patient at the very start of retrospective observation period, i.e. first recorded treatment combination in the study) will be tabulated by the below listed parameters using the generic table format below (see example tables: Table 10, Table 11, Table 12 and Table 6):

- Demographic data;
- Disease activity at Visits 1, 2, 3 (Mayo, Harvey-Bradshaw indices);
- Disease status assessed by investigator at Visits 1, 2, 3;
- Frequency (percentage) of clinical, endoscopic and histologic remission at Visits 1, 2, 3 and retrospective period of observation;
- Extent of lesion at Visits 1, 2, 3;
- Systemic (extraintestinal) manifestations at Visits 1, 2, 3;
- Total number, duration and severity of disease exacerbations by Visit 1, 2 and 3;
- Total number, type and duration of disease complications by Visit 1, 2 and 3;
- Laboratory and instrumental assessments at Visits 1, 2, 3;
- Percentage of patient with surgical treatment by Visits 1, 2, 3 grouped by:
  - Indication;
  - Surgery type;
  - Presence of complications.
- Number of surgeries by Visits 1, 2, 3;

Protocol ID	MACS-2017-102279	STATISTICAL ANALYSIS PLAN	Page 25 of 41	
IP	N/A		Date	30.12.2021
ID	MACS-2017-102279_SAP		Version	v1.2 final

- Percentage of patients with at least one episode of failure or biological or/and non-biological therapy (e.g., dose escalation of biologics, switching to another therapy, IBD-related surgery, medication augmentation) by Visits 1, 2 and 3;
- Separately for patients who achieved / not achieved T2T treatment goals (based on the clinical assessment of IBD) by Visits 1, 2 and 3:
  - Presence of therapeutic de-escalation;
  - Presence of therapeutic escalation;
  - Continuation of therapy without any changes.
- Healthcare resources utilization:
  - Hospitalizations due to complications;
  - IBD-related surgeries;
  - Percentage of patients that used healthcare resources;
- Only for biological therapy - percentage (by Visits 1, 2, 3) of patients with:
  - Positive test results for TB before the start of biological therapy;
  - Active TB before the start of biological therapy;
- Percentage of patients by Visits 1, 2, 3 with:
  - Reactivation of TB;
  - New occurrence of TB.

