**The same information will be provided for the treatment pattern (if the corresponding treatment pattern will be large enough to make statistical inferences).**

As treatment pattern change over time, patterns will be assessed for certain time points and the change of patterns will be tracked throughout the study (see also example Table 8):

- Retrospective treatment pattern (change assessment for every 6 months of the 2-year treatment interval);
- Treatment pattern between the date of enrollment and 6 months;
- Treatment pattern between 6 and 12 months.

Accordingly, for each above-mentioned period, each pattern will be assessed for the history of changes (see example Table 8):

- Presence of dose modifications;
- Presence of discontinuations / treatment changes;
- Presence of flares (during the course of treatment);
- Add-on therapy.

Protocol ID	MACS-2017-102279	STATISTICAL ANALYSIS PLAN	Page 26 of 41	
IP	N/A		Date	30.12.2021
ID	MACS-2017-102279_SAP		Version	v1.2 final

In order to track the history of transition of subject “states” (i.e. treatment using the certain pattern from the list above), in addition to the descriptive 6-monthly data, transition state (Sankey) diagrams will be built (see Figure 2 for mock example) to visualize the subject journey across patterns as well as trends of pattern change over time.

Treat-to-target (T2T) success will be assessed (in this SAP) using EDC data, based on the definition of failure to meet T2T goals (*lack of clinical and endoscopic remission based on investigator's feedback and objective methods of evaluation*). Overall T2T success or failure will be analyzed separately from this SAP using Investigator Survey data.

T2T treatment factors will be assessed by Visits 1, 2 and 3 and will be grouped by:

- Clinician-related factors:
  - Frequency and methods of assessment of UC/CD disease activity;
- Patient-related factors:
  - Demographic data;
  - Time frame between the date of first symptom(s) and the date of IBD diagnosis;
  - Smoking status;
- Disease-related factors:
  - Age of disease onset;
  - Location of disease;
  - Clinical course;
  - Disease severity;
  - Presence of intestinal and systemic (extraintestinal) manifestations;
  - Presence of complications;
  - Surgical treatment.

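### Endoscopic and combined clinical-endoscopic remission are, by default, estimated only in patients who had endoscopy, because percentages use non-missing observations and no rule covers endoscopy not done

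*SAP*

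**What the plan says.** **Endpoint.** SAP 6.1 lists as a secondary endpoint: "Percentage of moderate to severe IBD patients achieved clinical and combined clinical and endoscopic remission (based on T2T definitions"). The population named is all patients with moderate to severe disease, not those examined. SAP 8.1.3 tabulates it as "Frequency (percentage) of clinical, endoscopic and histologic remission at Visits 1, 2, 3 and retrospective period of observation".

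**Denominator.** SAP 8.1.1 presents qualitative data as a "frequency for the category (relative to the non-missing number of observations"), with exact or Goodman intervals. Protocol 15.2.1 agrees: "The frequency and percentages (based on the non-missing sample size) of observed levels will be reported for all categorical measures".

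**Availability of endoscopy.** The footnote to SAP Table 1 states: "All examinations results should be registered in electronic CRF only if they are done in routine practice". The V2 and V3 data list in SAP 5.3.2 has "endoscopic findings (if done").

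**Missing data.** Protocol 15.2.5 and SAP 8.4 plan neither imputation nor any assessment of missing-data patterns.

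**T2T failure.** SAP 8.1.3 defines it as "lack of clinical and endoscopic remission based on investigator's feedback and objective methods of evaluation". It does not say how to classify a patient who had no endoscopy.

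**Early leavers.** Protocol 15.2.4 says their last data will be collected and that "these cases will not be excluded from effectiveness analysis". SAP 5.4.2 also keeps their data in the final analysis. SAP 8.6 nevertheless allows patients or a whole centre to be left out at the analysis stage because of missing data.

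**The concern.** Endoscopy at a given time is the physician's choice, so patients with a result need not resemble those without one. If the non-missing rule is applied to endoscopic or combined remission as written, an endpoint defined over all patients is estimated in a subset selected by that choice. The confidence interval describes the same subset. SAP 8.1.4 prints the total including missing observations, which discloses the gap but changes neither the percentage nor its interval.

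This percentage answers the first part of the T2T objective. SAP 8.1.3 also tabulates treatment decisions separately for patients who did and did not reach T2T goals, which leaves unassessed patients without a defined group. SAP 8.1.1 further announces an exploratory search for significant associations between treatment patterns and outcomes. Different endoscopy use between treatment groups could create or hide such associations.

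**Working it through.** **The plan's own precision figure.** Protocol 15.4 assumes 2000 patients, 40% with Crohn's disease (CD), 40% on biologics and 10% drop-out: 2000 × 0.4 × 0.4 = 320, and 320 × 0.9 = 288. At a proportion of 50%, 1.96 × √(0.5 × 0.5 / 288) = 5.8 points, which matches the stated ±5.8%. That figure is for treatment failure. None is given for remission, and the documents give no endoscopy or remission rate, so every rate below is an assumption.

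**Effect on the denominator.** If 30%, 50% or 70% of the 288 have endoscopy, 86, 144 or 202 patients remain. With about 40% of them in combined remission (34, 58 or 81 patients), the Wald half-width is ±10.4, ±8.0 or ±6.8 points. Over all 320 enrolled, documented remission is 34/320 = 10.6%, 58/320 = 18.1% or 81/320 = 25.3%.

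**Selection example.** Assume clinical status is known for everyone, 50% are in clinical remission, and 60% of those are in endoscopic remission. The true combined rate is 0.5 × 0.6 = 30%. Let a be the share of clinical remitters scoped and b the share of non-remitters scoped.

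- Assessed only: (0.5 × a × 0.6) / (0.5a + 0.5b)
- Non-remitters counted as failures, unscoped remitters left missing: (0.5 × a × 0.6) / (0.5a + 0.5)
- Documented over all patients, which is the lower bound: 0.5 × a × 0.6
- Upper bound: the lower bound + 0.5 × (1 − a)

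| a / b | Assessed only | Non-remitters resolved | Documented, all patients | Feasible range |
|---|---|---|---|---|
| 50% / 50% | 0.15/0.50 = 30% | 0.15/0.75 = 20.0% | 15% | 15% to 40% |
| 30% / 60% | 0.09/0.45 = 20% | 0.09/0.65 = 13.8% | 9% | 9% to 44% |
| 60% / 30% | 0.18/0.45 = 40% | 0.18/0.80 = 22.5% | 18% | 18% to 38% |

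The assessed-only figure is right when endoscopy is unrelated to clinical status, and otherwise misses in either direction. In the last row it lies outside what the data permit. The third column shows that resolving non-remitters is not enough if unscoped remitters are then dropped from the denominator.

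**Early leavers.** With the documents' 10% drop-out and an assumed 50% remission in completers, the all-patient rate is 0.9 × 50% + 0.1 × L, where L is the rate in leavers. L = 0, 25% and 50% give 45.0%, 47.5% and 50.0%. The gap is at most 5 points if leavers do no better than completers.

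**The case against.** Several points limit the concern, and most of them stand.

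**It is a default, not an explicit rule for this endpoint.** Protocol 15.2.2 divides patients into those who reached remission and those who did not, with no unassessed category. T2T failure, worded as a lack of remission, could be read as counting undocumented patients as failures. Both readings are possible. The only denominator rule written down is the non-missing one, and the ambiguity itself needs resolving. The example tables in SAP 9.1, to which SAP 8.1.3 sends this output, were not in the text available here and may show the intended denominators.

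**A reader might infer that all remission percentages are affected.** They are not. Protocol 4.3 has partial Mayo or the Harvey-Bradshaw index evaluated at each visit, so clinical status does not depend on endoscopy. For CD, Protocol 4.4 also accepts cross-sectional imaging when ileocolonoscopy is inadequate.

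**A reader might infer very wide bounds by letting every unassessed patient count either way.** With 40% coverage and 50% success among those assessed, that gives 20% to 80%; with 60% coverage, 30% to 70%. These upper limits are wrong, because a patient not in clinical remission has failed the combined outcome without endoscopy. With 40% to 60% clinical remission among patients seen (assumed) and 10% of unknown status, the ceiling is 0.9 × 40% + 10% = 46% to 0.9 × 60% + 10% = 64%.

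**A reader might infer that early leavers are excluded.** Protocol 15.2.4 and SAP 5.4.2 say the opposite. What is missing is a rule for carrying this out.

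**Part of the remedy is already planned.** The frequency of assessment by each method is a secondary endpoint, and tables carry the total including missing observations. This helps the reader, but the reported percentage stays conditional on having been scoped.

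**The documents do not say what drives endoscopy use** beyond routine practice and the physician's decision. They therefore support no claim that one treatment group is favoured. Protocol 15.2.4 also concedes that effectiveness cannot be fully evaluated in this design.

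**Conclusion.** The concern holds for endoscopic and combined clinical-endoscopic remission. Followed as written, the non-missing rule estimates these in patients whose physician chose endoscopy, while the endpoint refers to all patients with moderate to severe disease. No stated rule covers the rest. In the example a true 30% is reported as 20% or 40%, depending on who is scoped. The size rests wholly on assumed rates, and the direction cannot be known in advance. The early-leaver gap is secondary.

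The endpoint is secondary and the study descriptive, so the sample-size figure is untouched. The change should still be made: it is a cheap improvement to the percentage that answers the T2T objective.

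**What to change.** For each disease and therapy group, the SAP should:

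- (a) report the share with endoscopy within a stated window or, for CD, with the imaging alternative of Protocol 4.4;
- (b) classify clinical non-remitters as not achieving combined remission, whether or not endoscopy was done;
- (c) report documented combined remission over all patients in the group, beside the assessed-only percentage labelled as such;
- (d) give lower and upper bounds in which only patients in clinical remission without endoscopy, or with unknown clinical status, move between not achieved and achieved;
- (e) state which last data represent early leavers, so that Protocol 15.2.4 and SAP 5.4.2 are carried out, and reconcile this with the exclusion allowance in SAP 8.6.

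The same derivation should fix T2T status for the treatment-decision tables. The cost is a few extra rows per table from data already collected, and an all-patient percentage that will look less favourable than the assessed-only one.

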15.2.5. Data handling

Missing data and invalid data

Missing data will not be restored. No procedures for missing data pattern assessment and/or imputation are planned.

Multiplicity

Because of descriptive nature of the study no multiplicity correction is applicable.

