#### 8.1.2 Assessment of primary endpoint

Treatment combinations will be described for UC and CD separately based on the following criteria:

- 1) Various types of biological and non-biological treatments including the following treatment combinations:
  - a. Steroid monotherapy (by class)
  - b. Steroids (by class) + immunosuppressive therapy (by class) combinations
  - c. Immunosuppressive monotherapy (by class)
  - d. Immunosuppressive (by class) + 5-aminosalicylic acid derivatives (by class)
  - e. 5-aminosalicylic acid derivatives monotherapy (by class)
  - f. TNF-alpha inhibitor monotherapy (by trade name)
  - g. TNF-alpha inhibitor therapy (by trade name) + steroids (by class)
  - h. TNF-alpha inhibitor therapy (by trade name) + immunosuppressive therapy (by class)
  - i. TNF-alpha inhibitor therapy (by trade name) + immunosuppressive therapy (by class) + steroids (by class)
  - j. Vedolizumab monotherapy (by INN)
  - k. Vedolizumab therapy (by INN) + immunosuppressive therapy (by class)
  - l. Vedolizumab therapy (by INN) + steroids (by class)
  - m. Vedolizumab therapy (by INN) + immunosuppressive therapy (by class) + steroids (by class)
  - n. Janus kinase (JAK) inhibitor monotherapy (by trade name)
  - o. JAK inhibitor therapy (by trade name) + steroids (by class)
  - p. JAK inhibitor therapy (by trade name) + immunosuppressive therapy (by class)
  - q. JAK inhibitor therapy (by trade name) + immunosuppressive therapy (by class) + steroids (by class)

---

 Steroids will be standardized through the calculation of prednisolone equivalent dose to facilitate comparisons between the classes

Protocol ID	MACS-2017-102279	STATISTICAL ANALYSIS PLAN	Page 24 of 41	
IP	N/A		Date	30.12.2021
ID	MACS-2017-102279_SAP		Version	v1.2 final

**Disclaimer:** due to the observational nature of the study, it is impossible to predict the distribution of treatment patterns before the actual analysis is performed. The list above can be modified based on the actual study data by excluding of certain combinations (absent in the database or identified in less than 25 subjects) or by including the combinations that were not initially planned but were identified in the actual study database.

Treatment pattern will include unique combination of certain treatments or treatment combinations along with their change over time.

Each treatment combination will be analyzed using the following summary data:

- Average course duration;

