### 8.3 Applicable significance level

Analysis will be performed in a descriptive manner, so, there will be no applicable statistical tests. However, 95% confidence intervals will be calculated for means and proportions, so, 95% significance level will be applied that corresponds to 5% alpha (type I) error.

As there are no statistical tests applied to any of the tabulated data, there will be no multiplicity (multiple comparison) corrections applied to the significance level.

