Retrospective and partial prospective data analysis (2020): will include the following endpoints (main endpoints will be assessed retrospectively for the period of 2 years of retrospective data collection and for the 6 months of the prospective data collection; safety endpoints will be assessed for prospective part of the study only):

- 1) Treatment patterns associated with prior biologic agents use or non-biological therapy according to the algorithm provided in the section 8.1.2);
- 2) Demographic data, medical history, treatment history, concurrent diseases, concomitant medications by treatment group/pattern;
- 3) Frequencies and time to achieve remissions and exacerbations by treatment group/pattern;
- 4) Frequency and methods of assessment of UC/CD disease activity;
- 5) Assessment of healthcare resource utilization;

Protocol ID	MACS-2017-102279	STATISTICAL ANALYSIS PLAN	Page 31 of 41	
IP	N/A		Date	30.12.2021
ID	MACS-2017-102279_SAP		Version	v1.2 final

- 6) Probable causes preventing achieving T2T targets during routine care;
- 7) The extent to which proposed Treat to Target goals are achieved by treatment group/pattern;
- 8) TB incidence and prevalence in IBD patients by treatment pattern;
- 9) TB medication's use in IBD patients by treatment pattern;
- 10) Adverse drug reactions (ADRs) on IBD treatments;
- 11) Adverse events on Entivyo® (vedolizumab) treatment;
- 12) Serious adverse events on IBD treatments (including Entivyo® (vedolizumab) treatment).

As there are no statistical hypotheses tested, there will be no alpha spending function correction applied to the interim analysis.

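### SAP 8.1.1 plans a search for statistically significant associations, while SAP 8.3 and 8.7 say nothing is tested and waive error control for that reason

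*SAP*

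**What the plan says.** **SAP 8.1.1** confines its statement on tests to one endpoint: "No statistical tests are planned for the primary endpoint of this study as all outputs will be purely descriptive". It then adds that "exploratory statistical analysis will be conducted to identify statistically significant associations between treatment patterns and outcomes".

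**SAP 8.3** speaks of the whole analysis: "Analysis will be performed in a descriptive manner, so, there will be no applicable statistical tests". It links the 95% intervals to an error rate ("95% significance level will be applied that corresponds to 5% alpha (type I) error") and concludes: "As there are no statistical tests applied to any of the tabulated data, there will be no multiplicity (multiple comparison) corrections".

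**SAP 8.7** reasons the same way for the interim looks: "As there are no statistical hypotheses tested, there will be no alpha spending function correction applied to the interim analysis".

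**Protocol 15.2.2** describes a descriptive approach and mentions no tests of association. **Protocol 15.2.5** waives correction on a different ground: "Because of descriptive nature of the study no multiplicity correction is applicable". **Protocol 15.2.4** accepts that an uncontrolled observational study cannot fully evaluate treatment effectiveness. **SAP section 3** requires any discrepancy with the protocol to be explained and justified.

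**The concern.** The SAP waives multiplicity control because it says nothing is tested. The search in 8.1.1 is testing by any ordinary meaning, so for that analysis the waiver has no basis.

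The search is also unconstrained. The SAP text available for review names no test or model for it, and gives no list of comparisons, adjustment set or reporting rule. SAP 8.1.2 lets combinations be added or dropped once the data are seen. Treatment follows routine practice, so patients on different patterns will differ at the outset, and some comparisons would involve the vedolizumab patterns.

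What is at stake is the standing of the secondary treatment-outcome results. Some could be called statistically significant with no stated control of error, in a study whose protocol says it cannot fully evaluate effectiveness.

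**Working it through.** **1. The statements side by side.**

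| Place | Scope | Position on tests |
|---|---|---|
| SAP 8.1.1, first statement | Primary endpoint | None |
| SAP 8.1.1, next sentence | Treatment patterns against outcomes | Search for significant associations |
| SAP 8.3 | Whole analysis | None, hence no correction |
| SAP 8.7 | Interim analyses | No hypotheses tested, hence no alpha spending |
| Protocol 15.2.2, 15.2.5 | Whole study | Descriptive; no correction applicable |

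Rows 1 and 2 can coexist because their scopes differ. Row 2 cannot coexist with row 3, and it conflicts with the premise in row 4. The protocol row is consistent within its own document; row 2 departs from it, and no rationale of the kind SAP section 3 requires was found.

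**2. Error level.** SAP 8.3 equates the 95% level with a 5% type I error: 1 − 0.95 = 0.05. This is the only error figure the plan gives. It does not state a number of tests, *m*, so *m* is an assumption below.

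**3. Input for the illustration.** SAP 8.1.2 lists 17 combinations (a to q), and "Treatment combinations will be described for UC and CD separately based on the following criteria".

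**4. One test per combination, one outcome.** If all nulls are true and the tests are independent, the chance of at least one false positive is 1 − 0.95^*m*.

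- One disease, *m* = 17: 1 − 0.95^17 = 0.582, with 17 × 0.05 = 0.85 expected false positives.
- UC and CD together, *m* = 34: 1 − 0.95^34 = 0.825, with 34 × 0.05 = 1.7 expected.

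**5. All pairs of combinations, one outcome, one disease.** The number of pairs is 17 × 16 / 2 = 136. If all nulls are true, 136 × 0.05 = 6.8 false positives are expected.

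**6. Sensitivity to the assumptions.** Smaller families give smaller rates: 22.6% for *m* = 5 and 40.1% for *m* = 10. Positive correlation between tests would lower the family-wise rates but leave the expected counts unchanged. The 17 is not fixed, because SAP 8.1.2 allows combinations seen in fewer than 25 subjects to be dropped and unplanned ones to be added.

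**7. Covariate timing, if the search is kept.** SAP 8.1.3 defines the original combination as the one in use when the two-year retrospective period begins. Disease activity data are scheduled at Visits 1, 2 and 3 but not retrospectively (Protocol 12.2; SAP Table 1). For a pattern that began in the retrospective period, Visit 1 activity is therefore measured after exposure started, and adjusting for it could remove part of the association being studied.

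**The case against.** The strongest defence is that the search is labelled exploratory, that exploratory work needs no formal multiplicity correction, and that 8.3 limits its waiver to tabulated data. The first two parts stand: correction is a choice here, not an obligation. The third does not, because the opening sentence of 8.3 excludes tests generally.

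Several stronger readings are tempting, but the documents do not support them.

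- *That the protocol shares the contradiction.* Protocol 15.2.5 rests on the study being descriptive, not on the absence of tests, and the protocol plans no significance search. The conflict lies within the SAP; the protocol matters as the document the SAP departs from without explanation.
- *That false positives will be reported as findings.* The SAP gives no reporting rule, so this is only a possibility.
- *That the analyses will be unadjusted.* The SAP is silent on adjustment and does not exclude it.
- *That 136 pairs or 6.8 false positives is what the plan would produce.* No section plans pairwise tests. A single global test per outcome is equally compatible with the text, and having every null true is unlikely across such different treatments.
- *That the count should be multiplied by the subgroup levels in SAP 7.4.* SAP 8.1.4 ties those subgroups to descriptive presentation. Many do not cross with all combinations: Harvey-Bradshaw bands apply only to CD, partial Mayo bands only to UC, and several groups are themselves defined by treatment.

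It is also fair to say that 8.1.3 lists the parameters to be tabulated by combination. That is a candidate set of outcomes, though the SAP does not say that the search is confined to it. The example tables in SAP section 9 were not available for this check, so a test specification there cannot be ruled out.

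**Conclusion.** The concern holds as an inconsistency within the SAP and an unexplained departure from the protocol. The reason given in 8.3 for omitting multiplicity control is untrue for the search planned in 8.1.1, and the premise in 8.7 conflicts with it too.

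The size is illustrative only: about 58% for at least one false positive per outcome with 17 independent tests at 5% and all nulls true, or 6.8 expected false positives if all 136 pairs were tested with all nulls true. The contradiction does not depend on these figures. It should be corrected because it governs what the study may claim about treatments and outcomes. The descriptive primary endpoint is not affected.

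**What to change.** **Preferred.** Delete the significance-search clause from SAP 8.1.1 and report estimates with 95% confidence intervals only. Sections 8.3 and 8.7 then stand, and the SAP again matches the protocol.

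**If the search is kept:**

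1. Correct 8.3 and 8.7 to say that tests are run, and give the rationale that SAP section 3 requires for departing from the protocol.
2. List the outcomes, the comparisons and the models.
3. Adjust only for covariates measured before the treatment pattern being analysed; do not use Visit 1 activity for patterns that began in the retrospective period.
4. Either control the false discovery rate within each disease, or label the results hypothesis-generating and drop the term statistically significant. Error-rate control does not deal with confounding, so item 3 is needed in either case.

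**Cost.** The preferred fix changes SAP wording only. Keeping the search adds the work of specifying and fitting the models. Either way, fewer results would be called significant. No data collection changes.
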